7.5 Baseline Data

Demographic and baseline variables whose information is available either at the preoperative or at the operative visit will be summarized using descriptive characteristics for continuous or categorical data:

- Demographics:
 - Age (in yr)
 - Gender

CONFIDENTIAL AND PROPRIETARY

This document contains information that is confidential and proprietary to Smith & Nephew PLC and Smith & Nephew, Inc. and is intended for use only by Smith & Nephew and its manufacturer. It shall not be reproduced or copied in whole or in part, nor shall the contents be disclosed by any means without prior written permission from Smith & Nephew, nor shall anyone make any use of it that is contrary to the expressed or implied wishes of Smith & Nephew

Statistical Analysis Plan	Smith+Nephew
A Prospective, Non-randomized, Multi-Center Investigation of All-suture-based Repair of Horizontal Meniscal Tears (STITCH Study)	Number: CTX-CP001
	Version: 1, 4-Sept-2019
	Page: 11 of 15

- Ethnicity
- Weight (in lb)
- Height (in inch)
- BMI (in kg/m²)
- Medical history:
 - Duration of symptoms before surgery (in wk)
 - Time since injury (weeks)
 - Primary diagnosis
- Pathology:
 - Side of tear (left knee, right knee)
 - Study meniscus compartment (medial, lateral)
 - Tear depth type (partial/complete and whether red/red-white/complete)
 - Rim width, deepest zone (Zone 1, Zone 2, Zone 3)
 - Posterior-Mid body-Anterior Location
 - Central to popliteal hiatus (Yes/No)
 - Quality of tissue (non-degenerative, generative, undetermined)
 - Length of tear (in mm)
 - Primary orientation (Horizontal/Oblique)
- Surgery details:
 - Surgery time (in min)
 - Anesthesiology Time (minutes)
 - Meniscal repair time (in min)
 - Completion of partial meniscectomy of the White Zone (Yes/No)
 - Medial/Lateral/Over-all percentages of the meniscus excised (in %)
 - Number of sutures used
 - Knot location (tibial, femoral, extra-capsular, others)
 - Surgical technique
 - Devices used
 - Suture configurations used

7.6 Disposition Data

The number of subjects that are screened, that entered the study, and that attended the study visits will be presented as numbers and percentages.

The reasons for study completion and withdrawals will be summarized. A listing of these reasons will be presented. The number of subjects that were prematurely terminated at the time of the 2-year analysis will be presented as number and percentage.

CONFIDENTIAL AND PROPRIETARY

This document contains information that is confidential and proprietary to Smith & Nephew PLC and Smith & Nephew, Inc. and is intended for use only by Smith & Nephew and its manufacturer. It shall not be reproduced or copied in whole or in part, nor shall the contents be disclosed by any means without prior written permission from Smith & Nephew, nor shall anyone make any use of it that is contrary to the expressed or implied wishes of Smith & Nephew

Statistical Analysis Plan	Smith+Nephew
A Prospective, Non-randomized, Multi-Center Investigation of All-suture-based Repair of Horizontal Meniscal Tears (STITCH Study)	Number: CTX-CP001
	Version: 1, 4-Sept-2019
	Page: 12 of 15

The study duration of all subjects will be summarized using descriptive characteristics for continuous variables (i.e. mean, median, SD, minimum, and maximum values).

Dates of first subject first visit and of last subject last visit will be reported.

7.7 Protocol Deviations

The frequency and type of protocol deviations will be summarized along with the number of subjects experiencing each.

7.8 Multiplicity

No adjustments for multiplicity are planned for this study.

7.9 Analysis of Primary Endpoint(s)

Freedom from re-operation of the index meniscus repair site:

The number and proportion of subjects experiencing freedom from reoperation of the index meniscus repair site at 6 months, 1 year, and 2 years will be presented together with a 95% confidence interval (calculated using the Clopper-Pearson Exact method ⁽¹⁾).

Logistic regression will be fitted to determine baseline predictors of freedom from re-operation success status. As a minimum the model will contain subject age and BMI. The following terms will be added to the model using a stepwise selection procedure with an F-value to attain a significance level of 0.1: tear compartment, circumferential length of tear, primarily horizontal vs. oblique, subject gender, study site, partial meniscectomy vs. no meniscectomy, and meniscal surgical technique.

Reoperations:

The number and proportion of patients requiring reoperations will be summarized and will be presented together with a 95% confidence interval (calculated using the Clopper-Pearson Exact method ⁽¹⁾).

CONFIDENTIAL AND PROPRIETARY

This document contains information that is confidential and proprietary to Smith & Nephew PLC and Smith & Nephew, Inc. and is intended for use only by Smith & Nephew and its manufacturer. It shall not be reproduced or copied in whole or in part, nor shall the contents be disclosed by any means without prior written permission from Smith & Nephew, nor shall anyone make any use of it that is contrary to the expressed or implied wishes of Smith & Nephew

Statistical Analysis Plan	Smith+Nephew
A Prospective, Non-randomized, Multi-Center Investigation of All-suture-based Repair of Horizontal Meniscal Tears (STITCH Study)	Number: CTX-CP001
	Version: 1, 4-Sept-2019
	Page: 13 of 15

Of those requiring re-operations, their time to re-operation will be summarized (using descriptive characteristics for continuous variables, i.e. mean, median, SD, minimum, and maximum values), along with the following:

- Surgery time (in min)
- Anesthesiology Time (minutes)
- Meniscal repair time (in min)
- Type of meniscal repair (Unicompartmental/Bicompartmental)
- Surgical technique (Inside-Out/Outside-In/All inside/Others)
- Device(s) used
- Completion of partial meniscectomy of the White Zone (Yes/No)
- Number of sutures used
- Suture configuration used (
- Knot location (tibial, femoral, extra-capsular, others)

Patient Reported Outcomes:

The patient reported outcomes (IKDC, KOOS Pain, KOOS Symptom, KOOS ADL, KOOS Sport, KOOS QOL, Lysholm, Tegner) will be summarized at each visit using descriptive characteristics for continuous variables (i.e. mean, median, SD, minimum, and maximum values). In addition, changes from baseline (Study Visit 1) to the subsequent follow-up visits will be similarly summarized. Results will be presented in narrative and graphically.

These measures will also be analyzed using inferential statistics. As appropriate, a repeated measure ANOVA or Wilcoxon signed rank test will be completed for each outcome measure. If a significant trend is identified, significance among time points, especially preoperative measures, may be further explored using the appropriate pair-wise comparisons. In all cases a p value equal to or less than 0.05 will be considered significant. Ninety-five percent (95%) CIs will be presented as well as corresponding p-values from the pair-wise comparisons of means from baseline to planned visits of interest (i.e. from Study Visit 1 to Day 90, Day 185, Day 365, and Day 730).

In addition, for Lysholm and/or IKDC, the numbers and proportions of subjects (out of total number of subjects providing data), together with a 95% confidence interval (calculated using the Clopper-

CONFIDENTIAL AND PROPRIETARY

This document contains information that is confidential and proprietary to Smith & Nephew PLC and Smith & Nephew, Inc. and is intended for use only by Smith & Nephew and its manufacturer. It shall not be reproduced or copied in whole or in part, nor shall the contents be disclosed by any means without prior written permission from Smith & Nephew, nor shall anyone make any use of it that is contrary to the expressed or implied wishes of Smith & Nephew

Statistical Analysis Plan	Smith+Nephew
A Prospective, Non-randomized, Multi-Center Investigation of All-suture-based Repair of Horizontal Meniscal Tears (STITCH Study)	Number: CTX-CP001
	Version: 1, 4-Sept-2019
	Page: 14 of 15

Pearson Exact method ⁱⁱⁱ, meeting the minimal clinically important differences (MCIDs) from baseline to Days 185 and 365 (MCID185_{IKDC}=6.3, MCID365_{Lysholm} =10.1, MCID365_{IKDC}=16.7) will be presented. There was no MCID for Lysholm at Day 185.

7.10 Analysis of Safety Endpoints:

All safety analyses and summaries will be done using the Safety Population.

The safety analyses will summarize the number (n) and percentages (%) of:

- the incidence according to subjects with at least one new complication,
- the incidence according to subjects with at least one new major complication,
- the incidence according to subjects whose complication was related to fall or injury,
- the incidence according to subjects who had at least one complication possibly, probably, or definitely related to surgical procedure,
- the incidence according to subjects who had at least one complication possibly, probably, or definitely related to meniscal repair, and
- the incidence according to subjects who had at least one complication possibly, probably, or definitely related to device(s) used.

A summary table will be presented that summarizes the complications by code according to subjects who had at least one new complication of a particular code.

In addition, for each complication, the following will be summarized: the relationship to the surgical procedure, the relationship to meniscal repair, the relationship to device(s) used, outcome and duration of the resolved complications and the duration of the complications at study discontinuation.

A listing of all new complications per subject will also be presented, along with duration, major complication status (yes/no), resolution status (resolved or ongoing), and relatedness to surgical procedure, meniscal repair, and device(s) used.

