9.2. Statistical Methods

Appropriate descriptive statistics will be presented for baseline characteristics, procedural variables, reoperation rate of the index meniscal repair site, and major complications. Logistic regression will be fitted to determine baseline predictors of various outcome measures. Independent variables for these models will include but may not be limited to, tear compartment, circumferential length of tear, primarily horizontal vs. oblique, subject age, subject gender, subject BMI, study site, partial meniscectomy vs. no meniscectomy, meniscal surgical technique.

Justification for data pooling will be made on a clinical basis.⁴⁸ These criteria call for use of the same protocol requirements at all sites, the sponsor to monitor the sites for compliance with the protocol, and the use of similar data collection procedures at all sites. Since this study does not include a control group, no analysis of the interaction of the treatment effect with clinical site is possible. Reoperation rates will be evaluated by clinical center.

Subject and reported outcome measures, KOOS, IKCD Knee Evaluation, Lysholm Knee Questionnaire and Tegner Activity Scale outcome assessments will be summarized and thoroughly characterized across time with the appropriate descriptive statistics including error measures. Statistics may include mean, mode, median, range, inter-quartile range, minimum, maximum and frequency, cumulative frequency percentage and cumulative percentage. Results will be presented in narrative and graphically.

These measures will also be analyzed using inferential statistics. As appropriate a repeated measure ANOVA or Wilcoxon signed rank test will be completed for each outcome measure. If a significant trend is identified, significance among time points, especially preoperative measures, may be further explored using the appropriate pair-wise comparisons. In all cases a p value equal to or less than 0.05 will be considered significant.

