6.1 Determination of Sample Size

There was no formal sample size calculation carried out for this clinical observational study because the study was not planned to test any formal hypothesis. Prior to the study commencement, it was planned to enroll 30 subjects into the study, and the sample size was accrued. However, a total of 3 subjects were excluded from all analyses for having met protocol deviations.

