7.1 General

Smith & Nephew's Global Biostatistics group will conduct the statistical analysis for this study. Unless otherwise stated, all significance tests and hypothesis testing will be two-sided, performed at the 5% significance level. Resulting p-values will be quoted and 95% two-sided confidence intervals will be generated where appropriate. All p-values will be rounded to three decimal places, p-values less than 0.001 will be presented as '<0.001' in all tables.

Where data summaries are specified, categorical and ordinal variables will be summarized with frequencies and percentages. Continuous variables will be summarized with the following summary

CONFIDENTIAL AND PROPRIETARY

This document contains information that is confidential and proprietary to Smith & Nephew PLC and Smith & Nephew, Inc. and is intended for use only by Smith & Nephew and its manufacturer. It shall not be reproduced or copied in whole or in part, nor shall the contents be disclosed by any means without prior written permission from Smith & Nephew, nor shall anyone make any use of it that is contrary to the expressed or implied wishes of Smith & Nephew

Statistical Analysis Plan	Smith+Nephew
A Prospective, Non-randomized, Multi-Center Investigation of All-suture-based Repair of Horizontal Meniscal Tears (STITCH Study)	Number: CTX-CP001
	Version: 1, 4-Sept-2019
	Page: 8 of 15

statistics: number of observations, mean, median, standard deviation, minimum and maximum values. All analyses will be performed in SAS 9.4 or later.

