7.3 Handling of Missing, Incomplete and Repeat Data

All data will be analyzed as observed cases unless otherwise indicated

CONFIDENTIAL AND PROPRIETARY

This document contains information that is confidential and proprietary to Smith & Nephew PLC and Smith & Nephew, Inc. and is intended for use only by Smith & Nephew and its manufacturer. It shall not be reproduced or copied in whole or in part, nor shall the contents be disclosed by any means without prior written permission from Smith & Nephew, nor shall anyone make any use of it that is contrary to the expressed or implied wishes of Smith & Nephew

Statistical Analysis Plan	Smith+Nephew
A Prospective, Non-randomized, Multi-Center Investigation of All-suture-based Repair of Horizontal Meniscal Tears (STITCH Study)	Number: CTX-CP001
	Version: 1, 4-Sept-2019
	Page: 9 of 15

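### The patient-reported outcomes are left to a choice between repeated-measures ANOVA and signed-rank; one pre-specified mixed model on all observed visits would serve better, with a modest and conditional gain

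*SAP*

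**What the plan says.** SAP 5.1 lists KOOS, IKDC, Lysholm and Tegner as primary endpoints beside freedom from reoperation. They are collected at screening and at Days 90, 185, 365 and 730. SAP 7.9 splits KOOS into five subscales, which makes eight scores.

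The inferential plan for these scores is one sentence in SAP 7.9: "As appropriate, a repeated measure ANOVA or Wilcoxon signed rank test will be completed for each outcome measure". Protocol 9.2 has the same sentence ("a repeated measure ANOVA or Wilcoxon signed rank test will be completed for each outcome measure"). Neither document gives a rule for choosing between the tests, a fitting procedure or a covariance structure.

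Both documents then make further pairwise comparisons depend on finding a significant trend. The SAP adds 95% intervals and p-values for mean change from baseline to each of the four follow-up visits. The threshold is fixed: "In all cases a p value equal to or less than 0.05 will be considered significant". SAP 7.1 makes tests two-sided.

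On missing data, SAP 7.3 has one line: "All data will be analyzed as observed cases unless otherwise indicated". On numbers, SAP 6.1 says "it was planned to enroll 30 subjects into the study, and the sample size was accrued", and then that "a total of 3 subjects were excluded from all analyses for having met protocol deviations". That leaves at most 27.

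Two other provisions matter. Protocol 5.3 withdraws subjects judged treatment failures and does not replace withdrawals. SAP 7.2 defines an Analysis Population that leaves out early withdrawers and is meant for supportive evidence on the primary variable. No population is explicitly assigned to the patient-reported outcomes.

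**The concern.** Neither named test fits the procedure around it well. Signed-rank handles one pair of measurements per subject, so it cannot give an overall test across five visits, and the trend step needs one. Nor does it yield an interval for a mean change. Repeated-measures ANOVA can give the overall test, but its classical form uses only subjects seen at all five visits. With at most 27 subjects, a few scattered missed visits would cost a noticeable share of the sample.

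Bias is also possible. Because treatment failures leave the study, later scores may be missing for a reason connected with outcome. An analysis of those who stayed could then describe a better-than-average group. A mixed model that uses every observed score can recover part of this, under conditions.

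**Working it through.** The plan states no power, SD, correlation or missed-visit rate, so there is no figure of its own to reproduce. Everything below except the subject counts and visits is an assumption.

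**Inputs.** From the documents: 30 − 3 = 27 subjects; five visits, four of them post-operative. Assumed: SD 18 points, true 2-year change 30 points, and a miss rate m of 5, 10 or 15% at each post-operative visit, independent between visits.

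**Step 1: subjects kept.** Complete cases = 27(1 − m)⁴. Available baseline-to-Day-730 pairs = 27(1 − m).

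| m | Complete cases | Available pairs |
|---|---|---|
| 5% | 27 × 0.815 = 22.0 | 25.7 |
| 10% | 27 × 0.656 = 17.7 | 24.3 |
| 15% | 27 × 0.522 = 14.1 | 23.0 |

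Independence is the unfavourable assumption. If the same subjects miss every visit, 10% missing leaves 24.3 complete cases, not 17.7.

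**Step 2: precision when misses are random.** Standard error (SE) varies as 1/√n, so the ratio of complete-case to available-pair SE is √[(1 − m)/(1 − m)⁴] = (1 − m)^(−1.5), which is 1.08, 1.17 and 1.28. Simulated SEs of the 2-year change, about 800 replicates each, with an unstructured likelihood fit as the mixed model:

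| Correlation | m | Complete case | Pairs | Mixed model | Complete case / mixed | Pairs / mixed |
|---|---|---|---|---|---|---|
| 0.5 | 5% | 3.79 | 3.58 | 3.55 | 1.07 | 1.01 |
| 0.5 | 10% | 4.39 | 3.66 | 3.64 | 1.21 | 1.01 |
| 0.5 | 15% | 4.91 | 4.01 | 3.87 | 1.27 | 1.04 |
| 0.7 | 5% | 3.12 | 2.88 | 2.85 | 1.09 | 1.01 |
| 0.7 | 10% | 3.38 | 2.84 | 2.80 | 1.21 | 1.01 |
| 0.7 | 15% | 3.76 | 2.88 | 2.84 | 1.32 | 1.01 |

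Over all runs made, the complete-case SE was roughly 7–9%, 20–24% and 27–38% larger than the mixed model's. The paired SE was about 0–4% larger.

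**Step 3: bias when withdrawal follows a low observed score.** Bias in the 2-year change, n = 27, correlation 0.7 between follow-ups, 5% intermittent misses added, about 700 replicates (Monte Carlo error about 5/√700 = 0.2):

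| Baseline-to-follow-up correlation | Withdrawal | Complete case | Pairs | Mixed, all subjects | Mixed, without early withdrawers |
|---|---|---|---|---|---|
| 0.2 | lower | +1.98 | +2.01 | +0.05 | +1.96 |
| 0.4 | lower | +1.17 | +1.25 | +0.12 | +1.24 |
| 0.2 | higher | +2.71 | +2.71 | −0.06 | +2.76 |
| 0.4 | higher | +1.70 | +1.56 | −0.11 | +1.55 |

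With n = 30 and lower withdrawal, the mixed model on all subjects gave +0.25 to +0.32, against +1.30 to +1.99 for the complete-case and paired estimates.

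**Step 4: where the advantage fails.**
- Equal correlations at all visits, same withdrawal mechanism: every method lay between −0.17 and +0.13, so there was no bias to remove.
- Withdrawal depending on the unseen next score, correlations 0.2 and 0.7: complete case +2.46, pairs +2.39, mixed model +1.26.
- The same with equal correlations: complete case and pairs +0.36 to +0.86, mixed model +0.83 to +1.61, which is worse.
- Compound symmetry in place of unstructured covariance, baseline correlation 0.3 and follow-up 0.7: remaining bias +0.8 to +1.5 where complete cases gave +1.5 to +2.9, so about half stays.

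**The case against.** A reader might infer that the SAP will delete every subject with a missed visit, contradicting its own observed-cases rule. The documents do not say so. They name no procedure, and a repeated-measures ANOVA can be fitted by likelihood to all observed visits, which agrees with SAP 7.3. The conflict arises only if the classical form is used.

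A reader might also infer that the test will be chosen after the results are seen. The SAP leaves the choice open but is silent on its timing, and the table shells it cites are not available here.

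The strongest objection concerns precision. The intervals that SAP 7.9 promises are baseline-to-visit contrasts, and each needs only two visits. Signed-rank tests of those pairs are equally workable. Against them a mixed model gains almost nothing when misses are random. That stands: the larger SE penalties apply only to a classical five-visit fit.

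It does not dispose of the point. Signed-rank still cannot perform the trend step, and in Step 3 the paired estimates carry the same bias as complete cases.

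It is also fair that this is a single-arm study with no formal hypothesis or sample-size calculation, and that descriptive summaries by visit are planned anyway. That limits the consequences, but the scores are labelled primary and will carry p-values.

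**Conclusion.** The point holds in limited form and is worth acting on. One of the two named tests cannot do what the next sentence requires. The other, in its classical form, is wasteful at this sample size. A mixed model on all observed visits is a better choice that needs no new data.

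Its size cannot be fixed from the documents. Under the assumed miss rates, a classical fit loses about 5 to 13 of 27 subjects (27 − 22 to 27 − 14), while against paired contrasts the precision gain is negligible. The avoidable bias is about 1–3 points on the 2-year change. It arises if withdrawal follows low observed scores and follow-ups correlate more with each other than with baseline.

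The broader claim that a mixed model is simply less biased is not supported. There is nothing to gain under completely random missingness or equal correlations, and it can do worse when withdrawal depends on unseen scores. The gain is also lost if the model is fitted on the Analysis Population, because early withdrawers have already been removed.

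**What to change.** In SAP 7.9, replace the open choice with the following.

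- **Model:** one mixed model for repeated measures per score, with baseline included as a response, visit as a categorical fixed effect, unstructured covariance, REML and Kenward-Roger degrees of freedom.
- **Estimates:** contrasts to baseline with 95% intervals at Days 90, 185, 365 and 730.
- **Population:** all treated subjects with any patient-reported score, not the Analysis Population. Say whether the three subjects excluded in SAP 6.1 belong to this set.
- **Fallback if the unstructured fit does not converge:** a structure that lets baseline-to-follow-up correlations differ from those between follow-ups, not plain compound symmetry. A one-factor analytic structure does this: loadings of √0.7 = 0.837 at follow-up and 0.3/0.837 = 0.358 at baseline give correlations of 0.7 and 0.3. It has 5 + 5 = 10 parameters, against 5 × 6/2 = 15 unstructured. Heterogeneous Toeplitz is a weaker candidate, because it forces equal correlations at equal lags.
- **Scores after reoperation or withdrawal for failure:** state how the analysis treats them. Left unstated, the model estimates what withdrawn subjects would have scored had they stayed in follow-up without failing.
- **Sensitivity:** an analysis allowing withdrawal to depend on unobserved scores, and signed-rank tests of each baseline-to-visit change. Signed-rank should be the main test for the ordinal Tegner scale.

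The cost is SAP wording, standard SAS code and a documented departure from protocol 9.2. The real downside is some convergence risk, with 15 covariance parameters and at most 30 subjects.
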